9.1 Inclusion Criteria

Stage 2:

Study group	Inclusion criteria
HC@H managers	
 Clinical or client care manager for HC@H at the time of the study. 18 years or older. Provide written, informed consent.
HammondCare Restorative Care Team AHPs	
 Physiotherapist, Occupational Therapist (OT), or Exercise Physiologist (EP) that are part of HammondCare's Restorative Care Team at the time of the study. 18 years or older. Provide written, informed consent.

Stage 3:

HC@H staff	
 • Care worker, clinical manager, or client care managers for HC@H at the time of the study. • 18 years or older. • Provide written, informed consent.
HammondCare Restorative Care Team AHPs	
 • Physiotherapist, OT, or EP that are part of HammondCare's Restorative Care Team at the time of the study. • 18 years or older. • Provide written, informed consent.

Stage 4:

HC@H clients	
 • Receiving community aged care services from HC@H at the time of the study. • 65 years or older. • Provide written, informed consent.
HC@H staff	
 • Care worker, clinical manager, or client care managers for HC@H at the time of the study. • 18 years or older. • Provide written, informed consent.
HammondCare Restorative Care Team AHPs	
 • Physiotherapist, OT, or EP that are part of HammondCare's Restorative Care Team at the time of the study. • 18 years or older. • Provide written, informed consent.

9.2 Exclusion Criteria

Stage 2:

Study group	Exclusion criteria
HC@H managers	
 • Participants that do not meet the inclusion criteria above. • Work outside of New South Wales (NSW), Australian Capital Territory (ACT), and Victoria.
HammondCare Restorative Care Team AHPs	
 • Participants that do not meet the inclusion criteria above. • AHPs other than those specified in the inclusion criteria. • Work outside of New South Wales (NSW), Australian Capital Territory (ACT), and Victoria.

Stage 3:

HC@H staff	
 • Participants that do not meet the inclusion criteria above. • Work outside of New South Wales (NSW), Australian Capital Territory (ACT), and Victoria.
HammondCare Restorative Care Team AHPs	
 • Participants that do not meet the inclusion criteria above. • AHPs other than those specified in the inclusion criteria. • Work outside of New South Wales (NSW), Australian Capital Territory (ACT), and Victoria.

Stage 4:

HC@H clients	
 • Participants that do not meet the inclusion criteria above. • Reside outside of New South Wales (NSW), Australian Capital Territory (ACT), and Victoria. • Insufficient English proficiency that prevents involvement in the virtual AHP falls risk assessment or survey. • Cognitive impairment that prevents their ability to provide informed consent. • Identified as at risk of falls and requires same day/urgent attention/referral as part of their usual care (e.g. urgent GP review due to a syncopal episode, same day review in the Emergency Department due to suspected head injury or fracture).
HC@H staff	
 • Participants that do not meet the inclusion criteria above. • Work outside of New South Wales (NSW), Australian Capital Territory (ACT), and Victoria.
HammondCare Restorative Care Team AHPs	
 • Participants that do not meet the inclusion criteria above. • AHPs other than those specified in the inclusion criteria. • Work outside of New South Wales (NSW), Australian Capital Territory (ACT), and Victoria.

9.3 Recruitment Strategy

Stages 2 and 3:

Stage 2 and 3 participants will be invited to be involved in this study through recruitment emails sent to HC@H staff and HammondCare Restorative Care Team AHPs via HC@H and HammondCare Restorative Care Team senior managers respectively, independent of the research team. Information on this study will also be provided to senior managers from within both the HC@H team and the HammondCare Restorative Care Team so it can be shared via internal team communications (e.g. staff/team meetings). Study information will include contact details of the research team to allow potential participants to ask further questions.

In addition for Stage 3, at the end of the Stage 2 focus groups participants will be provided with information on Stage 3 and invited to participate in the subsequent stage (review of the rapid-response falls risk assessment and management service tool and interview).

Stage 4:

HC@H staff (care workers, and clinical and client care managers) involved in Stages 2 and 3 of this study will be engaged to assist with recruitment of HC@H clients for Stage 4. They will receive training on the use of the falls risk stratification algorithm prior to recruitment. For instance, when the HC@H staff member observes a deterioration in the client's mobility or function during routine care, or is concerned that the client may be at an increased risk of falls (e.g. sustained a recent fall or near miss) they will deploy the falls risk stratification algorithm developed in this study. They will also ask the client if a HC@H clinical or client care manager who is not involved in their direct care can phone them to discuss participating in this study (Figure 2. HC@H client recruitment and consent process).

If the client provides verbal consent to be contact at the time the falls risk stratification algorithm is deployed, arrangements will be made for a HC@H clinical or client care (as appropriate) manager who is not involved in the direct care of the client to contact them via phone within 48 hours. Prior to the phone call, a Participant Information Sheet (PIS) will be provided to the client by HC@H staff so they can refer to it during the phone call. The HC@H clinical or client care manager will use the information available within the client's clinical notes and their own clinical judgement to initially screen the client (similar to how they would determine suitability of services in clinical practice). They will then complete the recruitment telephone call which would include discussion about this study, the client's potential participation in the study and what it would involve, completion/confirmation of screening questions, and gaining verbal, informed consent (provision of verbal consent will be audio recorded).

Where indicated (i.e. falls risk stratification algorithm identifies the client is at risk of falls), virtual delivery is possible (i.e. suitable virtual delivery device and connectivity available), and the client consents to participate in the study, clients will be offered participation in a virtually delivered AHP falls risk assessment (at no cost to the client). The virtual AHP falls risk assessment will be conducted by a HammondCare Restorative Care Team AHP, who will receive training on the use of the virtual AHP falls risk assessment prior to recruitment.

NOTE: For clients who are **not identified as being at risk of falls**, or who may have been identified as being at risk of falls but who **do not have the required connectivity** for a virtual assessment or **who chose not to participate** in the study, these clients **will receive usual care** by HC@H (which may variously include standard referral to allied health, liaison with the client's GP, liaison with family members, review by a HC@H clinical care manager).

[figure not shown]

Figure 2. HC@H client recruitment and consent process

HC@H staff and HammondCare Restorative Care Team AHPs that assist in the provision of the falls risk stratification algorithm or virtual AHP falls risk assessment (respectively) will be identified through review of the associated documentation within the clinical notes of Stage 4 client participants by a member of the research team. They will then be invited to participate in Stage 4 via a staff recruitment email sent via HC@H/HammondCare Restorative Care Team senior managers, independent of the research team. This email will include information about this stage of the study, the PIS, a link to the anonymous online survey, and the contact details of the research team to allow potential participants to ask further questions. The email will detail the steps the potential participant needs to follow if they would like to consent to participate in

this stage of the study (click on survey link, read the consent declaration [first page on weblink before starting survey], click the 'I agree, start survey' button at the bottom of the PIS page).

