Across Stages 2-4 HammondCare staff and clients will be enrolled in this study. HammondCare staff can consent to be involved in multiple stages. The target sample sizes for each stage are:

Stage 2:

Based on current literature, the target sample size is 18 (two to three focus groups of six to eight participants per group).¹² Ideally the sample size will be evenly distributed across the two participant groups: nine HC@H managers (a mix of clinical and client care managers), and nine HammondCare Restorative Care Team AHPs (a mix of physiotherapists, occupational therapists, and exercise physiologists).

Stage 3:

Based on other interview and survey studies, the target sample size is 22.¹² To ensure both components of the rapid-response falls risk assessment and management service tool are equally reviewed the sample size will be evenly split to include 11 HC@H staff (a mix of care workers, and clinical and client care managers) and 11 HammondCare Restorative Care Team AHPs (a mix of physiotherapists, occupational therapists, and exercise physiologists).

Stage 4:

The client target sample size is 13 HC@H community aged care clients, based on an anticipated referral rate of one per week (determined by staff feedback) over a three-month period. Potentially not all participants will require a virtual AHP falls risk assessment (dependent on the outcome of the falls risk stratification algorithm). To ensure sufficient data is collected for both components of the rapid-response falls risk assessment and management service tool a minimum of 50% of participants will need to have completed both the falls risk stratification algorithm and virtual AHP falls risk assessment. Therefore, recruitment will continue beyond the target sample size of 13 until the 50% minimum for completion of both components of the rapid-response falls risk assessment and management service tool is reached.

The staff target sample size is 13, based on recruitment of at least one member of staff per client participant (i.e. based on the falls risk stratification algorithm outcome for each client participant, a virtual AHP falls risk assessment may/ may not be indicated).

9. Selection and Withdrawal of Subjects

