9.5 Consent

Stages 2 and 3:

Stage 2 and 3 participants will be able to contact the research team to answer any questions they have before providing consent to participate in this study (using contact details provided in the recruitment email and information shared in staff/team meetings). At this time they will also be provided with a PISCF, and complete the screening questions (as outlined above in the *screening* section). They will have a one-week period to consider their participation and provide consent. This timeframe was considered sufficient whilst preventing delays in the completion of the study as both Stages 2 and 3 are required to inform subsequent stages and thus the development of the rapid-response falls risk assessment and management service tool. If they then decide to participate, they will be asked to sign and complete the consent portion of the PISCF (paper-based or electronic) and return it to the research team prior to data collection either by emailing it to the researchers or returning it to the researchers' office based at HammondCare (in person or the internal mail system).

Stage 4:

Consent from client participants will be obtain verbally by a HC@H clinical or client care manager who is not involved in the direct care of the client (Figure 2. HC@H client recruitment

and consent process). Verbal, informed consent will be obtained during a phone call to discuss the study and screen the client's eligibility, as a means of being able to deliver a rapid response virtual service (within 48 hours of client being identified as a potential participant for this study). Prior to this phone call, the PIS will be provided to the client by HC@H staff so the client has this to refer to during the phone call. This process will occur after the falls risk stratification algorithm developed in this study has been deployed by HC@H staff during routine care (as detailed above in the *recruitment* and *screening* sections). The confirmation of verbal consent by the client will be audio recorded, and then securely stored in the *verbal consent confirmation* folder. Consent will be reconfirmed by the client when they complete the online (or paper-based equivalent) survey by clicking the 'I agree, start survey' button at the bottom of the consent declaration page (first page) of the survey (this must be selected in order to start the survey).

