10.1 Trial Intervention

The trial intervention that will be piloted during Stage 4 will be developed in earlier stages (Stages 1-3) of the study, therefore it is not possible to detail specific components of the assessment intervention. However, both components of the rapid-response falls risk assessment and management service tool will be evidence-based on existing falls-related tools and best practice guidelines (i.e. neither component of the tool will be a new stand-alone development rather take a 'best of breed' approach). They will be developed based on existing

evidence of safety and efficacy, including consideration of tools most suitable for virtual assessments. The rapid-response falls risk assessment and management service tool will be administered by HC@H staff (falls risk stratification algorithm component) and HammondCare Restorative Care Team AHPs (virtual AHP falls risk assessment component), all of whom will receive training on the relevant component of the tool prior to Stage 4.

Following the virtual AHP falls risk assessment, the AHP will liaise with the client's HC@H clinical or client care (as appropriate) manager about their recommendations, which may include a virtually delivered falls program, a face-to-face AHP visit, liaison with GP or other usual care (all of which are currently available services from HammondCare and are not the subject of this research).

NOTE: For clients who are **not identified as being at risk of falls**, or who may have been identified as being at risk of falls but who **do not have the required connectivity** for a virtual assessment, or **who chose not to participate** in the study, these clients **will receive usual care** by HC@H (which may variously include standard referral to allied health, liaison with the client's GP, liaison with family members, review by a HC@H clinical care manager).

11. Safety and Monitoring

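### The Stage 4 staff survey reaches only staff recorded in enrolled clients' notes, so trained non-users, and users none of whose clients enrolled, are never asked

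*Protocol*

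**What the plan says.** Protocol 9.3 (Stage 4) defines who is surveyed. The people concerned are "HC@H staff and HammondCare Restorative Care Team AHPs that assist in the provision of the falls risk stratification algorithm or virtual AHP falls risk assessment". They "will be identified through review of the associated documentation within the clinical notes of Stage 4 client participants", and "They will then be invited to participate in Stage 4 via a staff recruitment email". The Protocol gives no other route into the Stage 4 staff survey.

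Training comes first. Section 9.3 says that "HC@H staff (care workers, and clinical and client care managers) involved in Stages 2 and 3 of this study will be engaged to assist" with client recruitment, and "They will receive training on the use of the falls risk stratification algorithm prior to recruitment". Section 10.1 says of those who administer either component: "all of whom will receive training on the relevant component of the tool prior to Stage 4".

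The algorithm is used before the client has consented. On the consent call, section 9.5 states: "This process will occur after the falls risk stratification algorithm developed in this study has been deployed by HC@H staff during routine care". Clients who do not take part go to usual care (9.3, 10.1).

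The Stage 4 staff criteria in 9.1 ask for a current role, adult age and consent. They do not ask for use of the tool. Section 8 adds that "HammondCare staff can consent to be involved in multiple stages".

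**The concern.** The research question in section 4 is about community aged care staff and AHPs in general: do they find the tool suitable, and can a service put it into practice? Section 7 makes fit with routine practice a focus of the pilot. A staff member who was trained but found no occasion, time or confidence to use the algorithm is direct evidence on both questions. So is one whose clients all declined or proved ineligible. The survey as framed hears from neither.

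If those staff see the tool differently from the staff who are reached, the suitability result describes a narrower group than the question names. The reasons for non-use, which a follow-on service would most need to know, are not collected. Part of the surveyed group may also have helped to shape the tool in Stages 2 and 3, and the Protocol mentions no survey item that would show this.

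**Working it through.** **1. The plan's own figures.** Section 8 sets 13 clients from one referral a week over three months: 1 × (365.25/12 × 3/7) = 13.04, so 13. It sets 13 staff from at least one per client: 13 × 1 = 13. Both reproduce.

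**2. Who is invited.** Reading 9.1, 9.3, 9.5 and 10 together:

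| Staff trained for Stage 4 | Invited? |
|---|---|
| HC@H staff with at least one enrolled client, including a client who completed only the algorithm | Yes |
| HC@H staff who used the algorithm, but only with clients who declined contact, refused consent or were ineligible | No |
| HC@H staff who never used the algorithm | No |
| AHPs who carried out at least one virtual assessment | Yes |
| AHPs who carried out none | No |

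A virtual assessment takes place only after the client consents, so an AHP is missed through non-use alone. HC@H staff can be missed through non-use or through client non-enrolment.

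**3. How many might be missed (illustration).** The number trained is not stated, so it is an assumption. Section 8 targets 9 HC@H managers in Stage 2 and 11 HC@H staff in Stage 3. With full overlap that is 11 people; with none it is 9 + 11 = 20. Assume also that each of 13 enrolled clients is equally likely to come from any trained HC@H member. For a pool of K:

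- expected number found in the notes = K × (1 − (1 − 1/K)^13)
- K = 11: 11 × (1 − (10/11)^13) = 7.81, so 29% are not invited
- K = 20: 20 × (1 − (19/20)^13) = 9.73, so 51% are not invited

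The missed share, (1 − 1/K)^13, rises with K. It also rises if clients cluster on a few staff. AHPs are not included in this calculation.

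**4. What coverage does to the result.** Let f be the share of trained staff reached, pU the proportion finding the tool suitable among those reached, and pN the proportion among those not reached. The survey differs from the all-trained figure by (1 − f) × (pU − pN). With pU = 80% (assumed):

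| f | pN = 40% | pN = 60% | pN = 80% | pN = 90% |
|---|---|---|---|---|
| 0.5 | +20 points | +10 points | 0 | −5 points |
| 0.9 | +4 points | +2 points | 0 | −1 point |

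The Protocol gives no value for f, pU or pN. Step 3 concerns f only. If staff were missed purely at random, pN would be expected to equal pU and the expected difference would be zero.

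**The case against.** The best defence is that surveying users is a legitimate way to measure user acceptance, which section 7 names as a focus, and that other measures cover part of the rest. Stage 2 focus groups and Stage 3 interviews collect staff views. Section 14 counts algorithm use and recruitment, so low uptake would be visible. This stands in part. User ratings should remain the main usability result. But the Stage 2 and 3 views come before live use, and usage counts show that a tool was not used without showing why.

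Four stronger readings are tempting and are not supported:

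- *Acceptability is biased upward.* That needs the missed staff to rate the tool lower. It is plausible, but nothing in the Protocol shows it, and random allocation by itself shows missing coverage, not bias.
- *The frame selects on success of the tool.* It selects on client enrolment. Section 8 expects some participants not to need the virtual assessment, and section 10 surveys clients after either component, so staff of consenting algorithm-only clients are reached. A user is missed only if none of their clients enrolled.
- *Staff whose at-risk clients lacked connectivity are never asked.* Section 9.3 sends such clients to usual care but does not say whether a consenting one stops being a participant. The text leaves this open.
- *Anonymity prevents separating those who helped in Stages 2 or 3.* An anonymous survey can ask about earlier involvement. The questionnaire is not in the Protocol, so it may already do so.

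The pool is also uncertain. Section 9.3 engages Stage 2 and 3 staff to help with recruitment, while 10.1 speaks of HC@H staff in general. Because 9.3 invites Stage 2 participants into Stage 3, the no-overlap end is the less likely one.

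**Conclusion.** The coverage gap is real and follows from the text alone: two groups of trained staff have no route into the survey that is meant to answer a question about staff suitability and deployment. The narrowing comes from the recruitment step, since 9.1 would admit them.

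The gap probably favours the tool, because the missed staff include those who met barriers. That is a judgement. Direction and size cannot be derived from the Protocol. The 29% to 51% not invited rests on an assumed pool of 11 to 20, Stage 2 and 3 targets being met, 13 enrolled clients and random allocation. It measures coverage, not bias.

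For a small descriptive pilot this does not threaten the study. It is a cheap improvement that would let the pilot learn why trained staff did not use the tool.

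**What to change.** In 9.3, replace identification through enrolled clients' notes with an invitation to every HC@H staff member and AHP trained for Stage 4. Send the same anonymous link through the same senior managers. Then:

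- Add one item on use of the component: used or not used, with the reason, including that the client declined or was ineligible.
- Add one yes/no item on involvement in Stage 2 or 3.
- Route non-users past questions that need experience of use.
- Report user ratings as the main usability result, with non-users' views on suitability and their reasons alongside.
- Give the number invited as the denominator.

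Eligibility in 9.1 does not change. Non-response remains, since 9.5 rules out reminders.

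The cost is a protocol amendment, a list of those trained (which should exist, as training precedes Stage 4) and two survey items. Little work is saved, because clinical records are still reviewed for pilot data. Ratings may be less favourable. With a staff target of 13, cells will be small, so breakdowns should be coarse enough to protect the anonymity promised to staff.

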9.4 Screening

Stages 2 and 3:

When potential participants contact a member of the research team to discuss their possible involvement in the study, the research team member will provide a PISCF and ask screening questions based on the inclusion and exclusion criteria. They will inform them of their eligibility or ineligibility to participate in the study at this time.

Stage 4:

HC@H clinical and client care managers will assist with screening of potential client participants in Stage 4. They will receive training on the screening process (including the inclusion and exclusion criteria) prior to the recruitment stage. When a client is identified as at risk of falls and could benefit from the falls risk stratification algorithm, they will also have the opportunity to be involved in this study (Figure 2. HC@H client recruitment and consent process). Recruitment will be completed by a HC@H clinical or client care manager who is not involved in the direct care of the client (as detailed in the *recruitment* section above). It is at this stage the HC@H clinical or client care manager will also screen clients if they are interested in participating in this study. They will first use the information available within the client's clinical notes and their own clinical judgement to determine if the client meets the study requirements (similar to how they would determine suitability of services in clinical practice), and then (re)confirm via the recruitment telephone call. They will inform the client of their eligibility or ineligibility to participate in the study at the time of the telephone call.

When potential HC@H staff and HammondCare Restorative Care Team AHP participants click the 'I agree, start survey' button at the bottom of the consent declaration (the first page of the survey) they will be taken to the screening questions (based on the inclusion and exclusion criteria). On completion of these questions they will be informed of their eligibility or ineligibility to participate in the study at this time. If they are eligible they will progress to the first survey question. If they are ineligible they will progress to the end page of the survey.

